3.3 Inclusion of Women and Minorities

- Both men and women of all races and ethnic groups are eligible for this trial.
 - Inclusion of Women and Minorities:
 - It is the intent of Lombardi Comprehensive Cancer Center to enroll patients regardless of gender or race. Both men and women of all races and ethnic groups are eligible for this study. In the development of this protocol, the possibility of inherent gender or racial/ethnic differences in treatment response has been considered.

4. REQUIRED DATA

4.1. Screening Phase

To be completed within 14 DAYS before Cycle 1 Day 1:

- All blood work

To be completed within 28 DAYS before Cycle 1 Day 1

- Any radiologic study (e.g., PET, CT, or MRI) that is utilized for tumor measurement
- History and physical

4.2. Schedule of Events

Table 1: Schedule of Events

All scheduled visits during Cycle 1 can occur +/- 1 day.

All scheduled visits during Cycles 2-12 can occur +/- 3 days if necessary.

For patients who continue on therapy after Cycle 12, scheduled visits and associated testing will occur every 2 cycles (instead of every cycle) with even numbered cycles only (i.e. Cycle 14, 16, etc.) All scheduled visits for patients receiving treatment after Cycle 12 can occur +/- 7 days if necessary.

As the bone marrow biopsy and aspirate are not needed to determine eligibility for trial enrollment, this test has been removed from the screening phase of the study. The bone marrow procedures must be performed after the patient has been provided an official identification subject number, but before the administration of the first dose of study drugs on Cycle 1 Day 1. The bone marrow biopsy at enrollment may be waived per investigator discretion. If a patient achieves a complete response by imaging, a bone marrow biopsy should be performed to confirm a complete response.

	Prior to Cycle 1 Day	Cycle 1 D1, 8, 15, 22	Cycle 2-12 Day1	Even Numbered Cycles after C12	At time of restaging*	Follow- up**
TESTS & OBSERVATIONS						
History and progress notes	X	X	A	X	X	X
Medication History	X	X	A	X	X	
Physical examination	X	X	A	X	X	X
Pulse, blood pressure	X	X	A	X	X	X
Height	X					
Weight/body surface area	X	X	A			
Performance status	X	X	A	X	X	X
Tumor measurements	X	B	B	B	B	B
Solicited baseline abnormalities/ adverse events assessment	X	X	X			
LABORATORY STUDIES						
CBC, differential, platelets	X	X	A	X	X	X
CMP, CrCl (estimated)	X	X	A	X	X	X
Uric acid, LDH, Mg, Phos, Ca	X	X	A	C	C	C
β2-microglobulin	X					
Serum or urine βHCG‡	X		A			
HBsAg, HBsAb, HB core Ab	X					
HCV antibody, HIV	X					
PT/INR, PTT	X					
EKG	X	C	C	C	C	C
Pharmacokinetics		X				
CORRELATIVE STUDIES						
Caris Life Sciences MI Tumor Seek	D					E

BCL-2 Protein Assessment	D				E
Tumor cell cultures	D				
STAGING					
PET-CT	X			X	F
CT/MRI (neck/chest/abd/pelvis)	X				X
Bone marrow aspirate & biopsy	G			H	
Histologic review	X				I

* Restage during week 12 (cycle 3), week 24 (cycle 6), and during week 52 (cycle 13).

** After week 52 of cycle 13, follow up every 6 months for 2 years, then every 12 months until disease progression or for a maximum of 10 years from study entry. If the patient ends treatment for any reason other than disease progression, follow up every 6 months until disease progression or for a maximum of 10 years from study entry. If disease progresses, follow up annually for a maximum of 10 years from study entry.

In the phase II portion of the study, patients who achieve a complete remission and electively discontinue therapy after 24 cycles will have a more frequent follow up schedule of every 3 months for a 1 year after discontinuation. Follow up consists of physical exam, labs, and imaging. After 1 year, they then resume follow up every 6 months for 2 years, then every 12 months until disease progression or for a maximum of 10 years from study entry. Patients may resume therapy for progression of disease or at the discretion of the investigator within one year of discontinuing therapy. If the patient resumes therapy within this time frame, study assessments should be performed as per Cycle 2 and beyond with the original restaging schedule. Patients will continue therapy until progression of disease or unacceptable toxicity.

‡ For women of childbearing potential.

A May be performed within 48 hours of Day 1

B If accessible to physical examination, record measurements.

C PRN

D To be performed on bone marrow sample after patient determined eligible and enrolled in study, but prior to administration of study drugs on Cycle 1 Day 1. If bone marrow not sufficiently involved with lymphoma, patient should be referred for a biopsy for the correlative studies or recent biopsy of another affected area may be submitted. Lack of marrow involvement does not impact patient eligibility. (Section 10).

E At the time of progression or relapse

F In the phase II portion of the study, patients who achieve a complete remission may discontinue therapy after 24 cycles. These patients must undergo a PET-CT during Cycle 24 to confirm they are in a complete remission prior to discontinuation.

G The bone marrow biopsy must be performed prior to administration of study drugs on Cycle 1 Day 1. The results are not needed for treatment unless the only indication for treatment is lymphomatous involvement of the bone marrow. Obtain 10 cc of aspirate (5 cc in EDTA tube, 5 cc in yellow citrate tube) and three centimeters of core. One centimeter of core and 5 cc of aspirate in an EDTA tube will be submitted to pathology for standard assessment for lymphomatous involvement. One centimeter of core and 5 cc aspirate in yellow tube will be submitted to HTSR. One centimeter of core will be submitted to Caris Life Sciences. See Appendix XII regarding sample submission. The bone marrow biopsy may be waived at investigator discretion.

H If initially positive, repeat only in patients who are in CR by all other criteria. If marrow is negative on one restaging biopsy, no subsequent bone marrow exam need be performed unless lymphoma has progressed clinically at another site. If bone marrow is still positive on restaging biopsy, it should be repeated at yearly intervals until determined to be negative. If not performed at enrollment, patients should undergo a bone marrow biopsy if imaging indicates a CR.

- I At time of progression or relapse, a biopsy of suspected area of involvement is recommended.

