1.3.2. Toxicology

No treatment-related effects were observed in the central nervous system or respiratory system in rats at any dose tested. In vivo safety pharmacology assessments performed in a cardiovascular study in telemetry-monitored dogs showed PR interval prolongation, lowered heart rate and shortening of QT interval corrected for heart rate (QTc). Based on data from rat and dog including general toxicity studies up to 13 weeks duration, the greatest potential for human toxicity with ibrutinib is predicted to be in lymphoid tissues (lymphoid depletion) and the gastrointestinal tract (soft feces/diarrhea with or without inflammation). Additional toxicity findings seen in only one species with no observed human correlate in clinical studies to date include pancreatic acinar cell atrophy (rat), minimally decreased trabecular and cortical bone (rat) and corneal dystrophy (dog). In studies in pregnant rats and rabbits, ibrutinib administration was associated with malformations (teratogenicity) at ibrutinib doses that result in approximately 14 and 2 times the exposure (area under the concentration-time curve [AUC]) in patients administered the dose of 560 mg daily, respectively. Fetal loss and reduced fetal body weights were also seen in treated pregnant animals. Carcinogenicity studies have not been conducted with ibrutinib. In vitro and in vivo genetic toxicity studies showed that ibrutinib is not genotoxic. No effects on fertility or reproductive capacities were observed in a study in male and female rats.

For the most comprehensive information regarding nonclinical safety pharmacology and toxicology, please refer to the current [IB](#).

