5.2. Treatment Plan

5.2.1 Phase I Study Treatment Plan

Patients will be treated with combination therapy of ibrutinib and venetoclax according to their assigned dose level cohort. Dose escalation is described in Table 2 and the paragraph below.

Each cycle is 28-days. Patients will be monitored for dose limiting toxicity (DLT) weekly during Cycle 1. Patients will receive the combination until progression or unacceptable toxicity. Patients will be followed during therapy through progression until next line of therapy. Questions regarding treatment should be directed to the Study Chair.

Table 2: Dose Level Cohorts

Dose Levels		
Dose Level	Ibrutinib	Venetoclax
0	420 mg	400 mg
1	560 mg	400 mg
2	560 mg	600 mg

*Dose Level 0 is the starting level dose

The MTD finding procedure starts at DL0. Three patients will initially be entered at this dose level.

- If 0/3 DLT is observed, dose escalation will continue to the next upper dose level.
- If $\geq 2/3$ DLTs are observed, then the dose finding procedure will be terminated.
- If 1/3 DLT is observed, then 3 additional patients will be enrolled in the same dose level. If no DLT is observed from the additional 3 patients, then dose escalation will continue to the next upper dose level. If any DLT is observed from the 3 additional patients, then the

previously lower dose will be chosen as the MTD and the dose finding procedure will be terminated.

Dose escalation will be continued as per Table 2 until a dose with no more than 1/6 DLTs is found and is chosen as the MTD. Once the MTD is determined, there will be a 17-patient phase II study at this dose level.

The original design of this study included a Dose Level 3 of Ibrutinib 560 mg and Venetoclax 800 mg. After examining the pharmacokinetic data at Dose Level 2, which showed a significantly increased systemic plasma exposure to ibrutinib, it was determined not to proceed with Dose Level 3. One patient had initiated therapy at Dose Level 3 before the decision was made for closure.

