5.2.2 Phase II Study Treatment Plan

Patients will be enrolled at the recommended phase II dose. Duration of therapy will depend on depth of response. Patients who achieve a complete remission may discontinue therapy after 24 cycles. These patients must undergo a PET-CT during Cycle 24 to confirm they are still in a complete remission prior to discontinuation. Patients who achieve a partial response will continue therapy until progression or unacceptable toxicity. Patients will be followed throughout the duration of therapy through progression until next line of therapy. Patients who achieve a complete remission and discontinue therapy after 24 cycles will be monitored closely per Table 1 and may be reinitiated on treatment within one year of discontinuation for either progression of disease or at the discretion of the treating physician.

Ibrutinib (capsules) and venetoclax (tablets) should be administered orally once daily at the same time. The capsules and tablets are to be taken at the same time each day with 8 ounces (approximately 240 mL) of water. The capsules and tablets should be swallowed intact and subjects should not attempt to open capsules or tablets or dissolve them in water. The first dose will be delivered in the clinic on Day 1, after which subsequent dosing is typically on an outpatient basis. All subjects must be trained to self-administer therapy orally 30 minutes after the completion of breakfast or the subject's first meal of the day. If a dose is not taken at the scheduled time, it can be taken as soon as possible on the same day with a return to the normal schedule the following day. Subject should not take extra capsules or tablets to make up the missed dose.

At study entry, patients will receive a Medication Calendar, and will be instructed on how to use the Medication Calendar. Study drugs will be dispensed to subjects in bottles at each visit. At monthly visits, the patient will bring the Medication Calendar to the clinic. All bottles of study medication (full, partial, and empty) should be brought to the clinic to compare with the Medication Calendar. The Medication Calendar for the previous month will be reviewed, and new Medication Calendar will be given to the patient (APPENDIX V). Unused study drugs

dispensed during previous visits must be returned to the site. Returned capsules and tablets must not be re-dispensed to anyone.

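### Table 1 leaves the pregnancy-test row blank after Cycle 12 and no other text clearly restores it, so daily dosing can continue for 364 days or more with no scheduled test

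*Combined protocol and SAP*

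**What the plan says.** In section 4.2, Table 1 has a row labelled "Serum or urine βHCG", footnoted to women of childbearing potential. It is marked before Cycle 1 and, with code A (within 48 hours of Day 1), for Cycles 2 to 12. The cells for even cycles after Cycle 12, restaging and follow-up are blank.

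The text above the table says that after Cycle 12 "scheduled visits and associated testing will occur every 2 cycles (instead of every cycle"), on even-numbered cycles only. It adds: "All scheduled visits for patients receiving treatment after Cycle 12 can occur +/- 7 days if necessary".

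Treatment runs well past Cycle 12:

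- Phase I (section 5.2.1): "Patients will receive the combination until progression or unacceptable toxicity".
- Phase II complete responders (section 5.2.2): "Patients who achieve a complete remission may discontinue therapy after 24 cycles".
- Phase II partial responders (section 5.2.2): "Patients who achieve a partial response will continue therapy until progression or unacceptable toxicity".

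Dosing is daily in 28-day cycles (section 5.2.1, Appendix V). A patient who stops electively after Cycle 24 and then resumes is covered separately: "study assessments should be performed as per Cycle 2 and beyond with the original restaging schedule".

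On fetal risk, section 1.3.2 states: "In studies in pregnant rats and rabbits, ibrutinib administration was associated with malformations (teratogenicity"). Section 13.4.3 requires a subject who becomes pregnant to stop study drug at once.

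**The concern.** The protocol tests once per cycle through Cycle 12 and then appears to stop, although exposure and the fetal hazard continue unchanged. No reason is given. The immediate-stop rule in section 13.4.3 works only if a pregnancy is found promptly. Without a scheduled test, detection after Cycle 12 rests on history and examination at the even-cycle visits and on the patient's own report. At stake is avoidable fetal exposure to ibrutinib, with venetoclax given alongside it.

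**Working it through.** **Does any text restore the test?** Five places could do so.

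- *Table 1, even-cycle column.* The column is itemised. Blood count and metabolic panel carry X, tumor measurements carry B, and uric acid/LDH/electrolytes and EKG carry C (as needed). The pregnancy-test row carries no mark.
- *Sentence above Table 1.* It moves the associated testing to every 2 cycles but does not name the tests. The column that lists them leaves this one out.
- *Section 3.1, item 10.* It requires a test at entry only.
- *Section 13.4.3.* It requires reporting and discontinuation but schedules no test.
- *Note on resumed therapy.* It applies only after an elective stop, so it does not cover a continuous course.

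None of the five clearly requires a test after Cycle 12 during continuous treatment.

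**Calendar check.** With 28-day cycles, the protocol's restaging calendar reproduces: 3 x 28 = 84 days = 12 weeks; 6 x 28 = 168 days = 24 weeks; 13 x 28 = 364 days = 52 weeks.

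**As written.** Study day of cycle c, day d = (c - 1) x 28 + d.

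- Scheduled tests through Cycle 12: 1 + 11 = 12. After that: 0.
- Cycle 12 Day 1 = 11 x 28 + 1 = day 309.
- Cycle 24 Day 28 = 23 x 28 + 28 = day 672.
- Dosing days from the last test through Cycle 24 = 672 - 309 + 1 = 364 (363 if the dose on the test day is not counted).
- Share of a 24-cycle course = 364 / 672 = 54%.

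**With the even-cycle column marked,** taking each visit as Day 1:

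- Added tests: Cycles 14, 16, 18, 20, 22 and 24 = 6.
- Interval between consecutive tests = 2 x 28 = 56 days nominal.
- Longest interval with +/- 7 days at both visits = 56 + 14 = 70 days.
- Interval from Cycle 12 to Cycle 14 with +/- 3 and +/- 7 days = 56 + 3 + 7 = 66 days, which is within the 70.
- The Cycle 14 test falls on day 13 x 28 + 1 = 365, so 56 of the 364 days pass before the first added test. The change can act on the other 364 - 56 = 308.

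**The case against.** The strongest objection is that the sentence above the table already carries the test forward. The test is done every cycle in Cycles 2 to 12, so moving associated testing to every 2 cycles would naturally include it. A blank cell in the even-cycle column is also weak evidence. The adverse-event row is blank there too, yet section 13.4.1 requires that assessment at every evaluation time point. This has weight: a reader might infer that the protocol categorically ends pregnancy testing at Cycle 12, and the documents do not go that far. What stands is that the text is unclear while the column is itemised. The blank adverse-event cell is covered by section 13.4.1; no section does the same for the pregnancy test.

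A second objection is that restaging in week 52 (Cycle 13) already draws blood and could carry a test sooner. It gains little: week 52 is days 358 to 364, and Cycle 14 Day 1 is day 365.

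A third is materiality. At most 35 patients are planned (section 12.4), median age at diagnosis is 60 (section 1.1.1), and highly effective contraception is required during therapy and for 30 days afterwards (section 3.1, item 11). This stands and keeps the priority low.

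A reader might also see a conflict between the serum-or-urine row label and the serum test required at entry. There is none to correct: item 10 governs entry, and a serum test satisfies both texts.

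**Conclusion.** The gap is real but minor. A site following Table 1 does no pregnancy test after Cycle 12 Day 1 during continuous treatment, and the sentence on testing every 2 cycles does not clearly change that. The untested period is up to 364 dosing days for a woman treated through Cycle 24. It is shorter if she progresses, withdraws or stops for toxicity, and has no fixed end for partial responders and phase I patients who stay on drug.

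A reader might set 364 days against the 28 dosing days that would follow a Cycle 24 Day 1 test. That overstates the gain, because 28 is only the tail after the last test. The relevant figure after the change is the longest untested interval: 56 days nominal, up to 70 with the windows.

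The figures assume 28-day cycles without delay and even-cycle visits on Day 1, a day that Table 1 does not state for them. The documents do not give the number of women of childbearing potential; it is likely small and could be zero. Nothing here affects the phase II error rates or the response estimate.

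**What to change.** In Table 1, mark the pregnancy-test row (serum or urine, women of childbearing potential) in the column for even-numbered cycles after Cycle 12.

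The cost is one table cell, plus six inexpensive tests per affected woman through Cycle 24 and one per two cycles after that. They fall at visits that already draw blood, so no visit is added. This is half the testing frequency of Cycles 2 to 12. Keeping monthly tests would need extra visits and is not proposed.

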Study Treatment:	
Phase I study:
 
Three patients will be enrolled at Dose Level 0 (DL0): Ibrutinib 420 mg daily and Venetoclax 400 mg daily. Each cycle is 28-days. Patients will be monitored for dose limiting toxicity (DLT) during Cycle 1. Patients will receive the combination until progression or unacceptable toxicity. Patients will be followed throughout the duration of therapy through progression until next line of therapy.
 
Dose Levels
 
  
 Dose Level	Ibrutinib	Venetoclax	
   
 0	420 mg	400 mg	
 
 1	560 mg	400 mg	
 
 2	560 mg	600 mg	
  
 
Phase II study:
 
Patients will be enrolled at the recommended phase II dose. Duration of therapy will depend on depth of response. Patients who achieve a complete remission may discontinue therapy after 24 cycles. These patients must undergo a PET-CT during Cycle 24 to confirm they are still in a complete remission prior to discontinuation. Patients who achieve a partial response will continue therapy until progression or unacceptable toxicity. Patients will be followed throughout the duration of therapy through progression until next line of therapy. Patients who achieve a complete remission and discontinue therapy after 24 cycles will be monitored closely with serial imaging and may be reinitiated on treatment within one year of discontinuation for either progression of disease or at the discretion of the treating physician.
	Dose Level	Ibrutinib	Venetoclax	0	420 mg	400 mg	1	560 mg	400 mg	2	560 mg	600 mg
Dose Level	Ibrutinib	Venetoclax											
0	420 mg	400 mg											
1	560 mg	400 mg											
2	560 mg	600 mg											
Participating Centers:	
MedStar Georgetown University Hospital Hackensack University Medical Center Seattle Cancer Care Alliance
												

ABBREVIATIONS

AE	Adverse event
AESI	Adverse events of special interest
ALT	Alanine transaminase
AML	Acute myeloid leukemia
AST	Aspartate transaminase
AUC	Area under the curve
BCR	B-cell receptor
BTK	Bruton-tyrosine kinase
CDUS	Clinical data update system

CI	Confidence interval
CLL	Chronic lymphocytic leukemia
C _{max}	Peak concentration
CR	Complete response
CRF	Case report form
CTCAE	NCI Common Terminology Criteria for Adverse Events
DCF	Data clarification form

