11.2. Withdrawal from Study Treatment

Each subject has the right to withdraw from the study at any time. In addition, the investigator will discontinue a subject from the study at any time if the investigator considers it necessary for any reason including:

- The investigator believes it is in the best interest of the subject;
- The subject's response to therapy is unsatisfactory, as evidenced by progression of disease while on study drug;
- The subject requires radiotherapy, cancer-related surgery as a result of tumor progression, or alternate anti-neoplastic agents during the study period;
- Noncompliance with the protocol;
- Unacceptable adverse event(s), or
- General or specific changes in the patient's condition render the patient unacceptable for further treatment in the judgment of the investigator.

If, at any time the constraints of this protocol are detrimental to the patient's health and/or patient no longer wishes to continue protocol therapy, protocol therapy shall be discontinued. In this event:

- Notify the Study Chair
- Document the reason(s) for discontinuation of therapy in the study record.
- Follow the patient for relapse, progression, survival, and secondary malignancies or new primaries.

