12.4. Target Accrual and Study Duration

The real sample size of this study is variable. The minimum required sample size is 6, but this number may change based on the number of DLTs experienced by patients during the phase I portion of the study. The maximum samples size will be 35 patients (= 3 dose levels x 6 patients + 17 patients for expansion). The patient accrual will be closed as soon as the MTD is found and the phase II expansion is completed. We will have conference calls every 2 weeks with all sites with patients enrolled to discuss toxicity in individual cases. The safety data of all patients will be reviewed during the biweekly conference calls, and the stopping rule for the 3+3 cohort scheme will be applied.

The estimated accrual rate is about 2 patients per month. As a result, it will take about 13 months to find and expand the MTD. However, observation of PFS will require longer follow-up. A maximum of 10 years of follow-up is required for all patients. Once the targeted number of patients has been accrued to this study, a notice suspending accrual will be issued to the Group via email broadcast announcing permanent termination of patient accrual within 14 days.

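### Treatment-plan text ends follow-up at next therapy while Table 1 continues it to 10 years, leaving overall survival censoring unsettled; a minor second point is that Kaplan-Meier PFS can read high between scans

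*Combined protocol and SAP*

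**What the plan says.** **End of follow-up.**

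- Synopsis (Study Treatment) and 5.2.2: "Patients will be followed throughout the duration of therapy through progression until next line of therapy". Section 5.2.1: "Patients will be followed during therapy through progression until next line of therapy".
- Table 1 footnote in 4.2: "If disease progresses, follow up annually for a maximum of 10 years from study entry". It does not name the next treatment as an end.
- Section 12.4: "A maximum of 10 years of follow-up is required for all patients".
- Section 11.2, where protocol therapy is discontinued because the protocol's constraints harm the patient or the patient no longer wants it: "Follow the patient for relapse, progression, survival, and secondary malignancies or new primaries".
- Section 13.4.4, on reporting new malignancies, takes for granted that survival is followed past progression.
- Section 12.2 defines overall survival (OS) from enrollment to death and plans a Kaplan-Meier estimate with a 95% confidence interval. It gives no censoring rule.

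**Timing of disease assessment.**

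- Table 1: "Restage during week 12 (cycle 3), week 24 (cycle 6), and during week 52 (cycle 13"; then "After week 52 of cycle 13, follow up every 6 months for 2 years, then every 12 months until disease progression".
- After stopping without progression: "If the patient ends treatment for any reason other than disease progression, follow up every 6 months until disease progression".
- Phase II complete responders who stop after 24 cycles have a Cycle 24 PET-CT, then visits with imaging every 3 months for a year.
- Section 12.2 estimates progression-free survival (PFS), from enrollment, by Kaplan-Meier. It does not say how a progression first seen on a scan is dated.

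**The concern.** The two follow-up rules cannot both be carried out for a patient who progresses and starts another treatment. Under one, the patient leaves follow-up; under the other, contact continues each year. Three centers take part, and nothing says which text prevails. The planned OS curve needs deaths that the shorter rule would not collect. Starting a new treatment is usually linked to prognosis, so censoring there would not be independent of the risk of death.

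For PFS, the scheduled scans leave 28 weeks uncovered in year 1, and later intervals are 6 and then 12 months. A progression in such a gap that is dated when it is found enters the Kaplan-Meier curve late. A value read between scans, or the median, then partly reflects the scan calendar. Sections 1.1.2 and 1.4.2 quote single-agent median PFS of 11 and 9.9 months, both inside the week 24 to 52 gap.

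**Working it through.** **Follow-up: the texts side by side.** Take a patient who progresses at month 8 and starts another treatment at month 9. Under the Synopsis, 5.2.1 and 5.2.2, follow-up ends at month 9. Under the Table 1 footnote it continues yearly, up to ten years from entry. A death at month 20 is an event under the footnote and a censoring at month 9 under the other wording. Only the footnote directly orders follow-up after progression for everyone. Section 12.4 supports it but mentions neither progression nor survival; 11.2 covers only the circumstances it lists; 13.4.4 presupposes survival follow-up rather than ordering it. The documents give no rate of next therapy and no survival figure, so the effect on OS cannot be calculated.

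**Plan's own figures.** The only computed design figures concern response. The exact two-stage calculation (at least 3 of 10, then at least 9 of 17) gives type I error 0.0402 and type II error 0.1992, against the stated 0.04 and 0.199. Nothing below enters it.

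**PFS: inputs.** Scans at weeks 12, 24 and 52 (Table 1); median 9.9 months (ibrutinib alone, 1.4.2). Assumed: an 18-month alternative, exponential PFS, progression dated at the scan that finds it, none found clinically, 30.4375 days per month. The lag from enrollment to Cycle 1 Day 1 is ignored.

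**Average excess, weeks 24 to 52.** With hazard λ = ln 2 / median in weeks and S(t) = exp(−λt), Kaplan-Meier stays at S(24) until week 52. The true average over the gap is [S(24) − S(52)] / (28λ).

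| Median | λ per week | S(24) | S(52) | True average | Excess |
|---|---|---|---|---|---|
| 9.9 months | 0.01610 | 0.679 | 0.433 | 0.547 | 13.3 points |
| 18 months | 0.00886 | 0.809 | 0.631 | 0.716 | 9.2 points |

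Scans every 12 weeks would still give [12·S(24) + 12·S(36) + 4·S(48)]/28 − 0.547 = 5.0 points at 9.9 months. About 8 of the 13 points therefore come from the long gap.

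**Single time points (median 9.9 months).**

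- At 9 months, an illustrative reading that the plan does not call for, the excess is 0.679 − 0.533 = 14.7 points. In simulation it falls to 8.7 if half of progressions are found at the next 28-day visit and to 5.7 if three quarters are.
- The binomial standard error there with 17 patients is √(0.5325 × 0.4675 / 17) = 0.121, or 12 points.
- Kaplan-Meier drops from 0.679 to 0.433 at week 52, so the reported median would be 12.0 months.
- Just after weeks 24 and 52, Kaplan-Meier equals S(24) and S(52): zero excess for patients on schedule.

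**Midpoint dating.** Progressions in the gap are dated at week 38. The average becomes (0.679 + 0.433)/2 = 0.556, an excess of 0.9 points. At 9 months (week 39.1) the curve reads 0.433 against 0.533, about 10 points too low.

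**Landmarks if early stoppers leave the week-based scans.** Simulated at a 9.9-month median, with stopping independent of progression and uniform over weeks 4 to 48, then scans every 26 weeks: 20% stopping gives about +2 points at week 24 and +3 at week 52; 40% gives about +4 and +6.5. If those patients keep the week 12, 24 and 52 scans, the excess is zero.

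**Interval-censored estimate with 17 patients (simulated, 40% stopping, week 52).** Kaplan-Meier error +6.1 (SD 11.8); Turnbull −0.1 (SD 12.7).

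**The case against.** The strongest defense is that the Table 1 footnote is the detailed schedule and 12.4 agrees with it, so sites would probably follow the longer rule and OS would be unharmed. A reader might infer from the conflict that OS will be biased. The documents do not support that: they show that one of two written instructions would cause it, not which one is followed. What stands is that the shorter rule is written three times, two of them in the treatment plan.

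On PFS the other side has more.

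- The endpoint is descriptive, is not a listed objective and carries no test; one standard error is about as large as the worst illustrative excess.
- Clinic visits between scans find some progressions, so the figures are upper bounds. Phase II complete responders who stop get extra imaging.
- A reader might infer that the landmark values are also too high. That requires 6-monthly follow-up to replace the week-based restaging after early stopping, which the text does not settle, and assumed stopping rates.
- A reader might suppose that no dating rule can help. Midpoint dating removes most of the average excess, though it overcorrects at some times.
- Nor is 28 weeks the longest interval in the plan: it is the year 1 gap, and follow-up later becomes yearly.

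All of this stands and makes the PFS part optional. It does not remove the direction of the error between scans, which the confidence interval does not show.

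**Conclusion.** The follow-up instructions contradict each other and are wrong as written. The effect on OS is zero if the Table 1 footnote is followed; otherwise neither its size nor its sign can be derived from the documents.

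The PFS point is minor. Under detection dating, exponential PFS and no clinical detection, Kaplan-Meier overstates PFS over weeks 24 to 52 by about 13 points on average at a 9.9-month median and 9 at 18 months. On-schedule values just after weeks 24 and 52 are unbiased under this model. Neither part touches the sample size or the response decision.

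**What to change.** 1. Reconcile the Synopsis, 5.2.1 and 5.2.2 with the Table 1 footnote so that survival follow-up continues after the next treatment begins. Add to 12.2: *OS is censored only at the last date known alive.* Cost: aligned wording in three places and one sentence; yearly contact after progression is already in Table 1.
2. Optional: in 12.2, report PFS at the week 24 and week 52 landmarks, read once those restaging assessments are complete and allowing for the lag from enrollment to Cycle 1 Day 1. State how progression is dated, and whether patients who stop early keep the week-based scans.
3. Optional: beside Kaplan-Meier, show a Turnbull estimate as a sensitivity analysis. Use each patient's last assessment without progression and first one showing it, with deaths as exact times and a bootstrap or similar interval.

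Items 2 and 3 cost a few sentences and one extra estimate, with no added scans. The Turnbull SD is up to about 1 point larger with 17 patients, and the median may have to be given as an interval. If everyone is on schedule and nothing is found clinically, it equals Kaplan-Meier at the landmarks and only displays the uncertainty between scans.
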